4.2.1 Primary Endpoints

a) Significant differences in Wilcoxon rank sum of ROC-optimized SC SPECT parameters will be tested between CTP classes. Spearman rank correlations between optimal SC SPECT parameters and clinical liver function parameters will be tabulated for the following categories: (1) composite liver function scoring systems (CTP score, ALBI grade), (2) individual quantitative liver function components (albumin, bilirubin, INR), and (3) individual qualitative clinical liver function components (encephalopathy, portal hypertension, ascites, and splenomegaly). Qualitative components will be treated as binary categorical variables (yes/no). Imaging and clinical parameters of liver function will be tested for association with overall survival. Continuous variables will be dichotomized above and below a threshold value that maximized accuracy of classification under ROC with balanced sensitivity and specificity. Univariate Cox proportional hazard regression will then be performed on all continuous and categorical variables. Statistically significant variables will serve as inputs into multivariate Cox proportional hazard regression. A stepwise backwards variable selection procedure will be followed to remove non-significant variables with high cross-correlation until the model log-likelihood is maximized.

Because radiomics generates feature sets of ~50 metrics, machine learning methods will be utilized to develop predictive models that are robust against overfitting, utilizing feature selection and classification/regression methods such as support vector machines, Bayesian analysis, and decision trees. These machine learning methods will be compared against standard statistical methods, such as ROC analysis and Kaplan-Meier estimation / Cox regression, for association to clinical liver function, prior liver-directed therapies, clinical outcomes (i.e. survival), and toxicity (i.e. CTP score progression).

b) The same set of statistical analysis will be performed for association of post-treatment changes in SC uptake on SPECT/CT imaging to clinical endpoints. Machine learning methods will test whether post-treatment changes in SC SPECT/CT provide independently predictive information after adjusting for baseline parameters.

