^{99m}Tc sulfur colloid single-photon emission computerized tomography (SC SPECT/CT) imaging is a well-established FDA-approved diagnostic imaging modality for the evaluation of hepatic function, introduced by Harper et al. in 1965 [16]. Colloidal particles such as SC are primarily taken up and cleared by the reticuloendothelial (Kupffer) cells that line the sinusoids of the liver and serve as supporting cells to hepatocytes, as well as the spleen and bone marrow. It has been established that a close correlation exists between the function of hepatocytes and Kupffer cells. Hepatocytes and Kupffer cells also exhibit similar perfusion characteristics, are equally affected by liver fibrosis, and are proportionately distributed within the liver [17, 18]. Furthermore, multiple studies have demonstrated that SC distribution within the liver correlates well with histology in explanted livers [19], presence and severity of cirrhosis [20], and long-term clinical outcomes of hepatic failure-related mortality [21]. SC function, therefore, can be used as a surrogate for hepatic function.

While SC SPECT/CT is well-suited for the proposed aims, there are other imaging options. HIDA (99mTc-acetanilide iminodiacetic acid) or mebrofenin SPECT is directly related to hepatocyte function [22], but HIDA is preferentially extracted to the bile ducts, producing distinct uptake patterns which would confound the proposed heterogeneity analysis. Additionally, HIDA protocols use dynamic SPECT, which presents challenges such as increased imaging time and analysis workload, uncertain impact of detector geometric dependence over the dynamic imaging course, and general limitations of image-based input functions for SPECT [23]. MRI tracers are of interest including Gd-EOB-DTPA, a hepatocyte-specific contrast agent [24, 25], as well non-specific Gd contrast, the perfusion of which may correlate to ICG clearance [26]. While promising, MRI is more problematic for radiomics and correlation with radiation dose maps due to the possibility of geometric distortion, susceptibility artifacts from implanted fiducial markers, and issues with quantitative accuracy and uniformity inherent to MRI.

Clinical Data to Date

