Detection of livery injury by radiation was first demonstrated in the late 1960's using 2-dimensional planar scintigraphy [27-29]. The inability to obtain 3-dimenstional spatial assessment of SC distribution in the liver and spleen hampered the routine use of SC in the clinic as well as application into the radiation and surgical oncology fields. Recently, the development of SPECT/CT technology has allowed improved regional contrast resolution relative to planar scintigraphy between functional, dysfunctional and non-functional liver from tomographic image acquisition, along with increased accuracy in local SC activity estimation from CT-based attenuation correction [30, 31]. Modern SC SPECT/CT imaging techniques, therefore, provide the potential for volumetric and spatial characterization of liver function prior to and in response to therapy. Preliminary retrospective data from our group have shown that measuring "total liver function" (derived from the product of functional liver volume and liver-to-spleen mean uptake) on pre-treatment SC SPECT/CT in 30 HCC patients may improve risk stratification and outcome prediction [32]. These data need to be validated prospectively with standardization of imaging protocols. Furthermore, changes in global or regional liver function as assessed with SC SPECT/CT, however, have not been studied in the context of RT and surgical resection of the liver.

Risks/Benefits

The primary risk to patients in this study is the risk associated with the two additional SPECT/CT ^{99m}Tc-SC scans. The radiation treatments or surgery that patients receive will be standard of care. Risks associated with the two SPECT/CT ^{99m}Tc-SC scans include: patient time (approximately 1 hour per scan); radiation dose from radioactive tracers and CT scans (up to ~ 30 mSv per session, which is about 0.1% of the usual radiation dose for liver cancer treatment, typically around 60 Gy), and intravenous injection and associated potential for bleeding, pain, infection, and injection site reaction.

In patients who opt to undergo the indocyanine green clearance study, there is the risk of art additional intravenous access procedure for the injection of the indocyanine green dye (injection of the indocyanine green must be separate from the intravenous access of the blood draw). Please see consent form for further details on potential risks.

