4.1.1 Primary Endpoints

a) In this study, patients with liver cancer will undergo SPECT/CT imaging with ^{99m}Tc-SC at the time of RT planning for cohort A and within 1-2 weeks prior to surgery for cohort B. All image datasets will be imported into MIM 6.0, and fused with the RT planning CT and radiation plan for cohort A and with the contrast-enhanced diagnostic CT or MRI scan.

To characterize whole-organ liver function, all pre-treatment SPECT/CT images will be analyzed for 1) ratios of maximum, mean, and total liver SC uptake relative to spleen SC uptake (L/S) and 2) volumetric SC parameters such as the functional liver volume (FLV) formed by 58% maximum image intensity threshold segmentation. Optimal image thresholds for SC SPECT parameter association to CTP classification (A vs. B/C class) will be interrogated by receiver-operator characteristic (ROC) analysis. Image thresholds that yield maximum AUC in quantitative parameters such as FLV ratio, L/S ratio, and their total liver function (TLF) product will be propagated to the remaining analyses. In cohort A receiving RT, planned dose-volume and dose-function metrics within the tumor-subtracted liver and functional liver volume(s) will

feature mean dose, $D_{xx\%}$ (the dose given to xx% of liver volume), V_{zz} (the liver volume which receives zz Gy), and fV_{zz} (the percentage of total liver function which receives zz Gy).

To characterize spatial distribution of functional liver, radiomics will be applied to SC SPECT/CT images via a locally-developed open source radiomics toolkit [33]. In addition to the whole-organ SC SPECT/CT metrics descried above, radiomic features will include intensity histogram features, along with a variety of textural features derived from co-occurrence matrices, neighborhood difference matrices, and zone size matrices [34-36].

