As a validation step, these baseline SC imaging data will be correlated to indocyanine green (ICG) clearance in patients (in those who opt to undergo this study), which assesses liver function based on the rate of clearance of a contrast agent over serial blood draws, and is considered a standard assessment of global liver function. ICG is a water-soluble compound that is selectively taken up by hepatocytes and transported into the biliary system without undergoing metabolism [37]. ICG clearance, therefore, can be utilized as an index of functioning hepatocyte mass [38] and is correlated with prediction of liver dysfunction and mortality associated with surgical resection [39]. The retention rate of ICG 15 minutes after administration (ICG-R15), a ratio of the ICG concentration at 15 minutes to its initial concentration in the blood, will be used to benchmark SC uptake metrics against. Higher ICG-R15 rates indicate worse liver function and would be expected to be correlated with lower global SC uptake metrics.

Functional FLR will be generated by calculating the volume of liver within the optimal image threshold as defined above. Anatomic FLR will be delineated and calculated on CT or MRI images using portal and hepatic veins as landmarks for segmental division. Logistic regression analyses and Pearson chi-square test will be used to compare the ability to predict for PHLR between functional FLR and anatomic FLR.

b) Correlate *post-treatment* changes in SC uptake on SPECT/CT imaging with changes clinical liver function. Relative changes in the parameters identified at baseline will be tested for correlation to changes in clinical liver function, including CTP score and ALBI grade, as well as their individual constituents.

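### The image threshold is tuned to CTP class and the tuned parameters are then tested against CTP class, apparently in the same patients, so the p-value is too small and the maximum AUC tends to be optimistic

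*Combined protocol and SAP*

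**What the plan says.** Section 4.1.1(a) describes the search. It covers every baseline scan: "all pre-treatment SPECT/CT images will be analyzed for 1) ratios of maximum, mean, and total liver SC uptake" relative to spleen uptake, together with volumetric parameters. One starting threshold is named: "functional liver volume (FLV) formed by 58% maximum image intensity threshold segmentation". The next sentence opens a search: "Optimal image thresholds for SC SPECT parameter association to CTP classification (A vs. B/C class) will be interrogated by" ROC analysis. The winners are then kept: "Image thresholds that yield maximum AUC in quantitative parameters such as FLV ratio, L/S ratio, and their total liver function (TLF) product" are the ones carried into the later analyses.

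Section 4.2.1(a) describes the test: "Significant differences in Wilcoxon rank sum of ROC-optimized SC SPECT parameters will be tested between CTP classes". The same item tabulates Spearman correlations of the optimised parameters with clinical liver function, including the CTP score.

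Section 1.0 (Statistical Methodology) mentions multi-fold cross-validation, but for prediction models. Section 4.2.1 brings in machine learning because radiomics yields about 50 features. Neither is attached to the image threshold or to the rank-sum test.

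**The concern.** The outcome that picks the threshold is the outcome then tested. A rank-sum p-value is valid for one parameter fixed before the CTP labels are used. Here it would be computed on the best of several candidates and read as if only one had been tried.

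The CTP comparison sits under primary endpoint (a) and is worded as a test of significance, so readers will take the p-value and AUC at face value. The Background already cites a correlation of sulfur colloid distribution with "presence and severity of cirrhosis". A complete absence of association is therefore unlikely, and the more practical harm is an overstated strength of association. A pilot's effect estimates are what later work tends to build on.

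**Working it through.** The plan states no alpha, power or expected AUC for this test, so there is no figure to reproduce.

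**Step 1: the algebra.** With n1 patients in B/C and n2 in A, AUC = U/(n1 × n2), where U is the rank-sum (Mann-Whitney) statistic. The group sizes are the same at every threshold, so the largest AUC is the largest U. Example with 15 in B/C (assumed) out of 60: n1 × n2 = 15 × 45 = 675. The null SD of the AUC is √[(60 + 1)/(12 × 675)] = √(61/8100) = 0.087. The upper rejection limit at two-sided 5% is 0.5 + 1.96 × 0.087 = 0.67. If any searched threshold exceeds 0.67 by chance, the selected one does.

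**Step 2: inputs.** From the documents: 60 patients (Section 4.0) and the A against B/C split (Section 4.1.1). Assumed: two-sided 5%; 10, 15 or 20 patients in B/C; 11 or 21 thresholds; normal marker values with AR(1) correlation of 0.90 to 0.99 between adjacent thresholds; search in the expected direction only. The last assumption fits the plan's expectation in Section 4.1.1 that worse function, measured there by ICG retention, "would be expected to be correlated with lower global SC uptake metrics".

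**Step 3: results per parameter.** Null simulations used 10,000 to 12,000 trials per cell. The bottom-line range also takes in repeat runs.

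| Adjacent correlation, thresholds | Type I error | AUC optimism if true AUC is 0.75 at every threshold |
|---|---|---|
| 0.99, 11 or 21 | 5.4–7.3% | 0.02–0.04 |
| 0.95, 11 | 7.8–8.2% | 0.04–0.06 |
| 0.95, 21 | 11.4–12.2% | 0.06–0.08 |
| 0.90–0.99, 11–21 (whole range) | about 5–18% | 0.02–0.10 |
| One fixed threshold | about 4–5.5% | 0 |

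- The upper end needs weakly correlated thresholds. Over 21 thresholds the end-to-end correlation is 0.90^20 = 0.12, 0.95^20 = 0.36 or 0.99^20 = 0.82.
- Refining the 11-point grid to 21 points over the same range (adjacent correlation √0.95 = 0.975) gives 8.2–9.1%. The width of the search matters more than the number of points.
- The two-sided figure at 0.99 looks mild partly because the search moves false positives into the expected direction. Those alone are 4.6–6.2% at 0.99, against 2.2–2.7% at a fixed threshold.

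**Step 4: AUC that is not flat.** Let the true AUC peak at 0.75 mid-grid and fall to 0.65 at the ends. Optimism is then about 0.00 to 0.10 against the true AUC of the chosen threshold, and about 0.00 to 0.06 against the best threshold (lowest cell −0.002). At correlation 0.99 it is 0.002 to 0.020 against the chosen threshold.

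**Step 5: Spearman with CTP score.** With assumed scores of 5 to 9, type I error is 5.1–13.5%, against 4.5–5.5% at a fixed threshold. The bias is of the same kind but smaller.

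**Step 6: do the corrections work?** Permutation with the search repeated each time gave 4.3–5.6% at nominal 5%. Five-fold cross-validation with the threshold re-chosen in each fold gave a mean AUC of 0.747–0.754 when the truth was 0.75, and 0.497–0.506 when it was 0.50.

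**The case against.** The strongest reply concerns size and importance. Thresholds on the same image are cut-offs of one intensity map and may be very highly correlated. In that case type I error is about 5 to 7%, close to nominal. No decision rule or power statement rests on the CTP test. The hypotheses under Section 3.1(a) concern survival, ICG clearance, future liver remnant and heterogeneity, so CTP acts largely as a tuning target. All of this stands and limits the consequence. It does not make the p-value valid, and objective (a) does include correlation with clinical liver function.

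Use of the same patients is inferred from silence. That is a fair caution, but the plan describes no second set of patients for this step. Section 4.2.1 also sets machine learning methods, meant to resist overfitting, beside ROC analysis. That comparison leaves the rank-sum p-value uncorrected.

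Three stronger readings are tempting, and the documents do not support them:

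- A reader might infer that a true AUC of 0.75 would necessarily be reported as 0.77 to 0.85. That requires the AUC to be equally good at every threshold, which the documents do not say.
- A reader might infer that the design defeats the validation promised in the Background: "These data need to be validated prospectively with standardization of imaging protocols". The retrospective data described there concern risk stratification and outcome prediction, not discrimination of CTP class.
- A reader might infer that every later analysis is inflated because the threshold is carried forward. ICG clearance and survival did not select the threshold. Any carry-over to them would be indirect, through their association with CTP class, and is not sized here.

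**Conclusion.** The point holds for the rank-sum test between CTP classes and for any maximum AUC reported with it, and to a lesser degree for Spearman correlations with the CTP score. That the p-value is too small follows from the algebra, given that the same patients are used. The size cannot be fixed from the documents: the ranges above rest on an assumed alpha, threshold grid, correlation and CTP split, and they apply to each parameter separately. Type I error could be barely above nominal or more than three times nominal (18/5 = 3.6), and the AUC optimism could be negligible or as much as about 0.10. The matter is of moderate weight: worth correcting before analysis, but no threat to the pilot as a whole.

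**What to change.** In Section 4.2.1(a), for every parameter whose threshold was chosen by AUC on CTP class, adopt one of two options and state the significance level and direction.

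- **(a) Keep the search and correct for it.** Report a permutation p-value that repeats the whole threshold search in each permutation of the CTP labels. With it, report a cross-validated or optimism-corrected AUC, with the threshold re-chosen in each training fold.
- **(b) Lock the threshold.** Test CTP at a threshold fixed before the data are seen, for example the 58% already named for FLV, stating whether it also applies to L/S and TLF. Label the optimised-threshold CTP test, its AUC and the Spearman correlations with CTP score exploratory.

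Neither option is generally more powerful. These comparisons used an upper-tail 2.5% level under the assumed models:

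| Situation | Locked threshold | Search plus permutation |
|---|---|---|
| Locked at the optimum (peak 0.75, ends 0.65 or 0.60) | 72–92% | 56–86% |
| AUC 0.75 at every threshold | 73–93% | 75–95% |
| Locked off-optimum (0.65 there, 0.75 at the best) | 31–49% | 55–82% |

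In the first situation the locked threshold won in all 24 cells. The documents do not show how close 58% lies to the optimum for CTP class, so the choice is the sponsor's.

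The cost is a few sentences and, for (a), a short program; no new patients or data are needed. The downside is less favourable p-values and AUCs than the uncorrected ones.

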Currently, evaluation of global liver function routinely incorporates conventional laboratory blood tests (e.g. bilirubin, albumin, coagulation factors) and clinical variables (e.g. presence of ascites or hepatic encephalopathy) that indirectly measure liver function. They form the basis of clinical scoring systems such as the Child-Turcotte-Pugh (CTP) system that characterize liver dysfunction. However, these assessment tools are susceptible to subjectivity (clinical assessment of degree or severity of ascites and hepatic encephalopathy) and confounding factors (malnutrition affecting albumin) and may be unreliable in predicting hepatotoxicity after liver-directed treatment [13]. Small changes in the component lab values, for example, can lead to more significant score changes that may not truly reflect liver dysfunction, and transition between CTP classes can have major impact on patient management.

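### Yes/no coding of ascites and encephalopathy ties slight with severe signs at baseline and, in the component-level change analysis, hides worsening in patients already positive

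*Combined protocol and SAP*

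**What the plan says.** Section 4.2.1, item (a), sets out three groups of clinical parameters for Spearman correlation with the SPECT metrics. The third is "individual qualitative clinical liver function components (encephalopathy, portal hypertension, ascites, and splenomegaly", and for this group the rule is "Qualitative components will be treated as binary categorical variables (yes/no". No severity grade is used.

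Item (b) of the same section covers change: "The same set of statistical analysis will be performed for association of post-treatment changes in SC uptake on SPECT/CT imaging to clinical endpoints". It gives no other coding for the clinical signs. Section 4.1.1(b) defines what the imaging changes are correlated with: "changes in clinical liver function, including CTP score and ALBI grade, as well as their individual constituents".

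Section 2.0 (Background) names ascites and hepatic encephalopathy among the variables behind scores such as CTP. It calls these tools "susceptible to subjectivity (clinical assessment of degree or severity of ascites and hepatic encephalopathy", so the protocol itself describes the two signs as assessed by degree. Section 4.2.1(a) also gives CTP score progression as the toxicity outcome.

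**The concern.** A yes/no variable keeps only the step from absent to present. At baseline, slight and severe disease share one rank, so the Spearman coefficient cannot use the ordering between them. For change, a patient with slight ascites before treatment and marked ascites at follow-up is yes on both occasions and looks the same as a patient who did not change.

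The patients affected are those with impaired livers at entry. They are expected in the study. Section 5.0 sets no liver-function limit and no limit on prior therapy, section 4.1.1(a) plans a contrast of CTP class A with B/C, and the hypotheses in section 3.1 concern less compensated livers and imaging change that tracks clinical change. A weak component-level correlation could then be read as a lack of association between SC decline and ascites when the coding is part of the cause.

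**Working it through.** The plan states no alpha, power, effect size or baseline prevalence for this analysis, so there is no figure of its own to reproduce. The check has four steps.

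**Inputs from the documents.** The yes/no coding and its reuse for change come from 4.2.1(a) and (b), change in CTP constituents from 4.1.1(b), and 40 patients in Cohort A and 20 in Cohort B from section 4.0. **Assumed inputs.** These are the baseline prevalence, the number of grades, and all the simulation parameters in step 4.

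**1. Ceiling.** Let b = 1 if the sign is present and 0 if absent, and let change = b(follow-up) − b(baseline). If b(baseline) = 1, change is 1 − 1 = 0 or 0 − 1 = −1. Its maximum is 0, so worsening cannot appear. The documents do not say how change in a yes/no sign is computed, but the other natural rules do no better. New onset is impossible for a patient already positive, and follow-up status is yes whether or not the sign has worsened.

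**2. Which transitions are lost.** Grade the sign 0 (absent) upwards.
- Three assumed levels: the worsening transitions are 0→1, 0→2 and 1→2. Yes/no coding loses 1→2, which is 1 of 3.
- Four assumed levels: there are six worsening transitions. Yes/no coding loses 1→2, 1→3 and 2→3, which is 3 of 6.

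These are kinds of transition, not frequencies.

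**3. Patients at the ceiling for a given sign** = assumed prevalence × n.
- Cohort A: 0.10 × 40 = 4; 0.40 × 40 = 16.
- Cohort B: 0.10 × 20 = 2; 0.40 × 20 = 8.

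Hidden worsening also requires the grade to rise by follow-up, so these are upper bounds on it for the assumed prevalence.

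**4. Illustrative power.** This is Spearman correlation of imaging change with change in the sign, two-sided 0.05, 1000 simulated trials per row. Assumptions: three levels cut from a normal severity scale, with the second cut 1 SD above the first; mean worsening 0.5 SD with a between-patient spread of 0.7 SD; latent correlation 0.5 between imaging change and worsening.

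| n | Assumed prevalence | Graded change | Yes/no change |
|---|---|---|---|
| 40 | 10% | 0.35 | 0.29 |
| 40 | 30% | 0.52 | 0.34 |
| 40 | 50% | 0.54 | 0.29 |
| 20 | 10% | 0.16 | 0.14 |
| 20 | 30% | 0.28 | 0.17 |
| 20 | 50% | 0.27 | 0.13 |

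The simulation standard error of one entry is at most √(0.25/1000) = 0.016. The gap is small at 10% prevalence and clear at 30–50%. It combines the ceiling with the coarser scale for new onset (0→1 and 0→2 score alike).

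**The case against.** The strongest reply is that the plan records this worsening elsewhere. Change in the composite CTP score belongs to the same endpoint, and toxicity is CTP score progression. Since the Background describes assessment of ascites and encephalopathy by degree, a rise in either can show in the composite. A reader might infer that a patient positive at baseline can never register worsening in the study; the documents do not support that. This part of the objection stands and limits the point to the component analyses. It does not remove the point, because the plan chose to tabulate components separately and the composite cannot show which one moved.

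Second, the Background treats subjective grading as a weakness, so yes/no coding could be deliberate. The plan gives no such reason, and the CTP score it analyses carries the same subjectivity. Likewise, Table 1 lists a physical exam only at screening and 1 month, so a grade at the first follow-up scan is not assured. That limits the CTP score at that scan equally.

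Third, splenomegaly. A reader might extend the point to it as a CTP constituent, or assume that spleen volume is already available from the liver-to-spleen ratios. No passage lists splenomegaly as a constituent of CTP or ALBI; it reaches the change analysis only through the general reuse in item (b). The ratios are specified for pre-treatment images, "ratios of maximum, mean, and total liver SC uptake relative to spleen SC uptake (L/S", with no statement that the whole spleen is outlined on every scan.

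Fourth, the plan never states the change rule, so a score of zero for yes-to-yes is an inference. That is correct, but step 1 shows that the ceiling does not depend on which natural rule is used.

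**Conclusion.** The point holds at component level. The baseline ties follow directly from the coding sentence. The ceiling on change follows by logic once the item (a) coding is carried into item (b), which the text implies and nowhere overrides.

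It is a minor point: one set of correlations in a pilot study with no stated power, alongside a composite score that can capture the same worsening. The 4–16 of 40 rests on an assumed prevalence of 10–40%. It should not be read as the number of patients whose worsening is missed; that number is not known and cannot exceed those at the ceiling. The power figures show direction and rough scale under stated assumptions and do not estimate what this study will lose.

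**What to change.** In 4.2.1(a) and (b), state that ascites and encephalopathy are analysed by the ordinal grade assigned for the CTP score, both at baseline and as change in grade. Spearman correlation takes ordinal data without modification.

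For signs kept yes/no (portal hypertension and splenomegaly), define change as new onset among patients negative at baseline, and report that denominator for each sign. For example, an assumed 10–40% baseline prevalence would leave 36 to 24 of 40 in Cohort A. Also state at which follow-up assessments the grades are recorded, since Table 1 does not list an exam at each scan.

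The cost is a few sentences and a case-report field for each grade; no new test or visit is needed for the assessments that already yield a CTP score. The downside is sparse top grades in cohorts of 40 and 20. A rule for merging adjacent grades, fixed before the data are seen, would handle that. Patients already at the top grade remain at a ceiling, but they are only a subset of those at the ceiling under yes/no coding.
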